WHO	World Health Organization
WOCBP	women of childbearing potential

1. INTRODUCTION

Influenza is a major cause of morbidity and mortality worldwide with the elderly being at highest risk of complications and death. Seasonal flu vaccines are designed to protect against infection and illness caused by the flu viruses research indicates will be most common during the flu season. “Quadrivalent” flu vaccines are formulated to protect against four flu viruses, but do not protect against infection and illness caused by other viruses that can also cause flu-like symptoms. There are many other viruses besides flu viruses that can result in flu-like illness (also known as influenza-like illness) that spread during the flu season. These non-flu viruses include rhinovirus (one cause of the "common cold") and respiratory syncytial virus, which is the most common cause of severe respiratory illness in young children, as well as a leading cause of death from respiratory illness in those aged 65 years and older.

Fluzone Quadrivalent is a vaccine indicated for active immunization for the prevention of influenza disease caused by influenza A subtype viruses and type B viruses contained in the vaccine (1). It is approved in US for use in persons 6 months of age and older.

Antibody protection is traditionally measured by hemagglutinin-inhibition (HAI), where antibodies to the virus block the function of hemagglutinin to prevent viral attachment to host cells. It is believed that HAI antibody levels closely correlate with virus neutralization assays, however, it should not be considered a marker of efficacy (2).

The Safety profile of the Quadrivalent vaccine is similar to seasonal flu vaccines made to protect against three viruses, with similar mild side effects (injection site pain, malaise, headache).

This study is being undertaken to evaluate antibody and cellular immune responses to various influenza strains following seasonal influenza vaccination. Blood samples collected at 1 week and at various intervals up to 6 months post vaccination will be analyzed for assessment of cellular and antibody responses to the vaccine. Nasopharyngeal swabs collected at baseline and 4 weeks following immunization will be used to assess mucosal antibody response to influenza.

1.1 Study Rationale

The rationale for the study is to evaluate immunological responses to Fluzone Quadrivalent vaccine.

1.2 Risks and Benefits for Study Subjects

There will be no direct benefit for study subjects from receipt of the study drug. Indirect benefits to the subjects enrolled in this study are the free medical tests received at Screening and during the study.

The safety monitoring practices employed by this protocol (i.e., AE monitoring) are standard and considered adequate to protect the subjects' safety.

The total volume of blood that will be collected from each subject during this study is about 201 mL (see [Section 15.1](#)). For this 6-month study, the volume of blood collected from healthy adults is considered to be safe.

Anticipated risks of Fluzone Quadrivalent include injection site pain, myalgia, headache and malaise.

1.3 Population, Route, Dosage, Dosage Regimen, Treatment Period

The study population will be composed of male and female subjects, 18 to 50 years of age, inclusive, with a BMI ≤ 35 kg/m². Refer to Section 4 for details regarding the study population.

All subjects will be administered a single intramuscular dose of approved Fluzone Intramuscular Quadrivalent vaccine. Refer to Section 5 for details regarding study treatment.

1.4 Compliance Statement, Ethics and Regulatory Compliance

This study will be conducted in compliance with the protocol, the ethical principles that have their origin in the Declaration of Helsinki, the International Council for Harmonization (ICH) consolidated Guideline E6 for Good Clinical Practice (GCP) (Committee for Proprietary Medicinal Products [CPMP]/ICH/135/95)⁵, and the following regulations and guidance:

United States (US) Food and Drug Association GCP Regulations: Code of Federal Regulations (CFR) Title 21, Parts 11, 50, 54, 56, and 312⁶, as appropriate

The Health Insurance Portability and Accountability Act (HIPAA)⁷

Other applicable local regulations

1.4.1 Subject Confidentiality

The Investigator and the Sponsor will preserve the confidentiality of all subjects taking part in the study, in accordance with GCP and local regulations.

The Investigator must ensure that the subject's anonymity is maintained. On the Case Report Forms (CRFs) or other documents submitted to the Sponsor, subjects should be identified by a unique subject identifier as designated by the Sponsor. Documents that are not for submission to the Sponsor (e.g., signed informed consent forms [ICFs]) should be kept in strict confidence by the Investigator and designee.

In compliance with Federal regulations/ICH GCP guidelines, it is required that the Investigator and institution permit authorized representatives of the company, of the regulatory agencies, and the Institutional Review Board (IRB) direct access to review the subject's medical and study records for verification of study-related procedures and data. The Investigator is obligated to inform the subject that his/her study-related records will be reviewed by the above-named representatives without violating the confidentiality of the subject.

1.4.2 Informed Consent Procedure

Before a subject's participation in the study, it is the Investigator's and designee's responsibility to obtain freely given consent, in writing, from the subject after adequate explanation of the aims, methods, anticipated benefits, and potential hazards of the study and before any protocol-specific screening procedures or any study drugs are administered. The written ICF should be prepared in the local language(s) of the potential subject population.

In obtaining and documenting informed consent, the Investigator or designee should comply with the applicable regulatory requirements, and should adhere to GCP and to the ethical

principles that have their origin in the Declaration of Helsinki. The consent form and any revisions should be approved by the IRB prior to being provided to potential subjects.

The subject's written informed consent should be obtained prior to his/her participation in the study, and should be documented in the subject's medical records, as required by 21 CFR Part 312.62. The ICF should be signed and dated by the subject, and by the person who conducted the informed consent discussion (the Investigator or designee). The original signed ICF should be retained in accordance with institutional policy, and a copy of the signed consent form should be provided to the subject or legal representative. The date that informed consent was given should be recorded on the CRF.

If the subject cannot read, then according to ICH GCP Guideline, Section 4.8.9, an impartial witness should be present during the entire informed consent discussion. This witness should sign the ICF after the subject or the legally acceptable representative has orally consented to the subject's participation and, if possible, signed the ICF. By signing the ICF, the witness attests that the information in the ICF and any other written information was adequately explained to and apparently understood by the subject or the legally acceptable representative and that informed consent was freely given by the subject or the legally acceptable representative.

Additional consent is required for all subjects, in accordance with HIPAA. Subjects will consent to virology testing (including human immunodeficiency virus [HIV] antibody, hepatitis B surface antigen [HBsAg], hepatitis C virus [HCV] antibody) as part of their initial informed consent. This testing will be described in the ICF.

1.4.3 Regulatory Compliance

The study protocol, subject information, consent form, Product Insert, any or written instructions to be given to the subject, available safety information, subject recruitment tools and procedures (e.g., advertisements), information about payments and compensation available to the subjects, and documentation evidencing the Investigator's or designee's qualifications should be submitted to the IRB for ethical review and approval according to local regulations, prior to their implementation. The written approval should identify all documents reviewed by name and version.

Changes in the conduct of the study or planned analysis will be documented in a protocol amendment.

The Investigator or designee must submit and, where necessary, obtain approval from the IRB for all subsequent protocol amendments and changes to the informed consent document or changes of the investigational site, facilities, or key personnel. The Investigator or designee should notify the IRB of deviations from the protocol or SAEs occurring at the site and other AE reports received from the Sponsor or Contract Research Organization (CRO), in accordance with local procedures.

2. STUDY OBJECTIVES

2.1. Primary Objective

The primary objective of this study is:

To evaluate the antibody response as measured by HAI following administration of the approved Fluzone Intramuscular Quadrivalent vaccine.

2.2. Secondary Objectives

The secondary objectives of this study are:

To evaluate antibody responses to divergent influenza strains following seasonal influenza vaccination

To evaluate cellular immune responses following seasonal influenza vaccination

To evaluate mucosal antibody responses following seasonal influenza vaccination

3. STUDY DESIGN

3.1. Overall Plan

3.1.1. Study Type

This is a phase 4, single center, open-label, study designed to collect blood and nasopharyngeal samples from subjects who received a single intramuscular injection of the FDA approved 2016-2017 quadrivalent influenza vaccine.

Prior to any study procedures being conducted, all subjects will be required to sign an ICF after having the study medication and requirements of the protocol fully explained. Prior to and after immunization, blood and nasopharyngeal swabs will be collected for HAI and cellular immune response and mucosal antibody response testing, respectively.

3.1.2. Treatment Groups

All subjects will receive one dose of the vaccine and there is only one treatment group.

Details for each study visit are provided in the study procedures (see [Section 6](#)) and in the Schedule of Events (see [Section 15.2](#)).

3.1.3. Study Endpoints

3.1.3.1. Immunogenicity Endpoints

Antibody and cellular immune responses following seasonal influenza vaccination

3.1.3.2 . Safety Endpoint

Adverse events

3.1.4. Duration of the Study

The duration of the study will be approximately up to 7 months.

3.1.5. Duration of Subject Participation

The duration of the study for each individual subject will be approximately up to 7 months from the start of Screening (within 28 days of dosing) through the final study visit. Dosing will be on a single occasion, followed by blood sampling up to 6 months post dose.

3.2 Selection of Dose

The dose of the vaccine to be administered (0.5 mL) is approved by FDA (see [Section 15.3](#)).

4. STUDY POPULATION

4.1. Enrollment

The Investigator will maintain a confidential screening log of all potential study candidates that includes limited information of the subjects (initials, age, sex), date, and outcome of screening process (e.g., enrolled in the study, reason for ineligibility, refused to participate).

Investigator will be expected to maintain an enrollment log of all subjects enrolled in the study indicating their assigned study number.

Investigator will maintain a confidential subject identification code list. This confidential list of names of all subjects allocated to study numbers upon enrolling in the study allows the Investigator to reveal the identity of any subject when necessary.

4.2. Inclusion and Exclusion Criteria

Subjects must satisfy all of the following criteria to be included in the study:

Inclusion Criteria

1. Men and women 18 to 50 years of age, inclusive
2. Good general health status, as determined by the Investigator
3. Adequate venous access for repeated phlebotomies
4. Screening laboratory results within institutional normal range or Grade 1 elevation if the Investigator documents clinical insignificance. Bilirubin may be Grade 2 if associated with normal alanine aminotransferase (ALT) and aspartate aminotransferase (AST) and the Investigator considers the result not to be clinically significant (e.g. vigorous exercise or Gilbert's syndrome)
5. Negative drug and alcohol screen at Screening and predose on Day 1
6. For women of child bearing potential (WOCBP), negative pregnancy test
7. Willingness to practice a highly effective method of contraception that may include, but is not limited to, abstinence, sex only with persons of the same sex, monogamous relationship with a postmenopausal partner, monogamous relationship with vasectomized partner, vasectomy, surgical sterilization (hysterectomy, or bilateral tubal ligation, salpingectomy, or oophorectomy), licensed hormonal methods, intrauterine device (IUD), or consistent use of a barrier method (e.g., condom, diaphragm) with spermicide for 28 days after the Fluzone Intramuscular Quadrivalent vaccine dose
8. Willingness to participate and comply with all aspects of the study through the entire study period, including nasal swabs and blood and urine samples
9. Provision of written informed consent

Exclusion Criteria:

1. Pregnant, possibly pregnant, or lactating women
2. Body mass index $> 35.0 \text{ kg/m}^2$
3. Positive results for HIV, hepatitis B virus, or hepatitis C virus at Screening
4. Asthma or other chronic lung disease that is greater than mild in severity. Specifically excluded are participants with any of the following events in the past year:
 - Daily symptoms
 - Daily use of short acting beta 2 agonists
 - Use of inhaled steroids or theophylline
 - Use of pulse systemic steroids
 - Emergency care or hospitalization related to asthma or other chronic lung disease
 - Systemic steroids for asthma exacerbation
5. History of diabetes mellitus (gestational diabetes is allowed if treatment was not required postpartum and serum glucose is currently in the normal range)
6. History of coronary artery disease, arrhythmia, or congestive heart failure
7. Clinically significant ECG abnormality
8. Poorly controlled hypertension (systolic blood pressure $> 150 \text{ mmHg}$ or diastolic blood pressure $> 95 \text{ mmHg}$) at Screening or predose on Day 1
9. History of anaphylaxis or angioedema
10. Known allergy to any of the ingredients in the vaccine formulation, including egg allergy
11. History of chronic rhinitis, nasal septal defect, cleft palate, nasal polyps, or other nasal abnormality that might affect vaccine administration
12. Previous nasal surgery or nasal cauterization
13. Any symptoms of upper respiratory infection or temperature $> 38^\circ\text{C}$ within 3 days before Day 1
14. Significant nasal congestion or rhinorrhea as assessed by the investigator.

15. Known or suspected malignancy, excluding non-melanoma skin cancers and other early stage surgically excised malignancies that the Investigator considers to be exceedingly unlikely to recur
16. Immunocompromised individuals, including those who have used corticosteroids (including intranasal steroids), alkylating drugs, antimetabolites, radiation, immunomodulating biologics, or other immunomodulating therapies within 90 days before Day 1 or those who plan use during the study period
17. Use of statin medication within 30 days before Day 1 (including atorvastatin, fluvastatin, lovastatin, pravastatin, rosuvastatin, simvastatin, pitavastatin)
18. Receipt of intranasal medications (including over-the-counter medications) within 30 days before Day 1
19. Receipt of any IP within 30 days before Day 1
20. Receipt of any vaccine within 30 days before Day 1
21. Receipt of intranasal vaccine within 90 days before Day 1
22. Receipt of any influenza vaccine within 6 months before Day 1
23. Any change in medication for a chronic medical condition within 30 days before Day 1
24. Past regular use or current use of intranasal illicit drugs, or any illicit drug by any route
25. Use of tobacco products or electronic cigarettes within 30 days before Day 1, or smoking of any type, including marijuana
26. Any medical, psychiatric, or social condition or any occupational or other responsibility that in the judgment of the Investigator would interfere with or serve as a contraindication to protocol adherence, assessment of safety (including immunogenicity), or a subject's ability to give informed consent

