6. STUDY PROCEDURES

A study visit schedule in tabular format is provided in [Table 15.2](#).

The Screening phase will take place on Day -28 through Day -1.

The following activities and/or assessments will be performed:

Day -28 through Day -1

- Informed consent
- Medical/surgical history, demographics, and eligibility criteria
- Physical examination including height, weight, and BMI
- Urine drug screen (opiates, benzodiazepines, amphetamines, cocaine, barbiturates, phencyclidine), and alcohol breath test
- Virology blood test including HIV antibody, HBsAg, HCV antibody
- Urine pregnancy test for WOCBP
- Clinical laboratory tests for serum chemistry, hematology, and UA
- Vital signs recorded after at least 5 min in the supine position consisting of pulse, diastolic blood pressure (DBP), systolic blood pressure (SBP), and oral temperature
- 12-Lead ECG
- Record prior/concomitant medications
- AE monitoring

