15.3. Package Insert Fluzone Quadrivalent

Sanofi Pasteur

450/477 Fluzone® Quadrivalent

HIGHLIGHTS OF PRESCRIBING INFORMATION

These highlights do not include all the information needed to use Fluzone® Quadrivalent safely and effectively. See full prescribing information for Fluzone Quadrivalent.

Fluzone Quadrivalent (Influenza Vaccine) Suspension for Intramuscular Injection 2016-2017 Formula

Initial US Approval (Fluzone Quadrivalent): 2013

INDICATIONS AND USAGE

Fluzone Quadrivalent is a vaccine indicated for active immunization for the prevention of influenza disease caused by influenza A subtype viruses and type B viruses contained in the vaccine. (1)
Fluzone Quadrivalent is approved for use in persons 6 months of age and older. (1)

DOSAGE AND ADMINISTRATION

- For intramuscular use only (2)

Age	Dose	Schedule
6 months through 35 months	One or two doses ^a , 0.25 mL each	If 2 doses, administer at least 4 weeks apart
36 months through 8 years	One or two doses ^a , 0.5 mL each	If 2 doses, administer at least 4 weeks apart
9 years and older	One dose, 0.5 mL	-

^a 1 or 2 doses depends on vaccination history as per Advisory Committee on Immunization Practices annual recommendations on prevention and control of influenza with vaccines

“-” Indicates information is not applicable

DOSAGE FORMS AND STRENGTHS

Suspension for injection supplied in 4 presentations: prefilled single-dose syringe (pink plunger rod), 0.25 mL; prefilled single-dose syringe (clear plunger rod), 0.5 mL; single-dose vial, 0.5 mL; multi-dose vial, 5 mL. (3)

LE687

CONTRAINDICATIONS

Severe allergic reaction (e.g., anaphylaxis) to any component of the vaccine protein, or after previous dose of any influenza vaccine. (4)

WARNINGS AND PRECAUTIONS

- If Guillain-Barré syndrome (GBS) has occurred within 6 weeks following influenza vaccination, the decision to give Fluzone Quadrivalent should be based on careful consideration of the potential benefits and risks. (5)

ADVERSE REACTIONS

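### No eligibility criterion, Screening item or Day 1 item in the protocol names Guillain-Barré syndrome, although the appended label warns about it: a minor, cheap safety improvement

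*Protocol*

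**What the plan says.** **Label.** Under Warnings and Precautions, the Highlights of the package insert in Protocol 15.3 state: "If Guillain-Barré syndrome (GBS) has occurred within 6 weeks following influenza vaccination, the decision to give Fluzone Quadrivalent should be based on careful consideration". The sentence goes on to say that the potential benefits and risks are what must be considered. GBS is not listed under Contraindications, where only severe allergic reaction appears.

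**Benefit.** Protocol 1.2: "There will be no direct benefit for study subjects from receipt of the study drug". The anticipated risks named there are local and mild systemic reactions. GBS is not among them, although the list is worded as open.

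**Criteria closest to the point (Protocol 4.2).**
- Exclusion 22: "Receipt of any influenza vaccine within 6 months before Day 1". Exclusions 20 and 21 set shorter windows: 30 days for any vaccine and 90 days for an intranasal one.
- Exclusion 16 covers immunosuppressive treatment, "or other immunomodulating therapies within 90 days before Day 1 or those who plan use during the study period".
- Exclusion 10: "Known allergy to any of the ingredients in the vaccine formulation, including egg allergy". Exclusion 9 bars a history of anaphylaxis or angioedema. Neither has a time limit.
- Inclusion 2: "Good general health status, as determined by the Investigator".
- Exclusion 26 covers any condition that "in the judgment of the Investigator would interfere with or serve as a contraindication to protocol adherence", assessment of safety or the ability to consent.

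**Procedures.** The Screening list in Section 6 has the general item "Medical/surgical history, demographics, and eligibility criteria". On Day 1 (6.3.1) subjects are asked whether the same criteria still hold. The examination in 10.7 covers the neurologic system at Screening and is repeated before dosing.

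**The concern.** The protocol gives a marketed vaccine and attaches its label. That label singles out one past event, GBS soon after an influenza vaccination, as a reason to stop and weigh benefit against risk. The protocol's own criteria and visit lists contain nothing that brings this event to the Investigator's attention.

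This matters more here than in routine care. The label asks for a balance, and Section 1.2 puts no direct benefit on one side of it, so little speaks for dosing a healthy volunteer with this history. An Investigator can weigh only what is known, and a general history question may not bring up an episode from which the volunteer recovered years ago. What is at stake is subject safety and an equal decision for every volunteer. No estimate, test or endpoint is affected.

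**Working it through.** The plan gives no figure to reproduce. The check sets the label warning against every place in the protocol where it could have been put into practice.

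**1. Criteria that name GBS.** Inputs: 9 inclusion and 26 exclusion criteria, in the synopsis and in 4.2 (9 + 26 = 35). Number naming GBS or any neurologic reaction to an earlier vaccine: 0 of 35 in either place. The only named past reactions are anaphylaxis, angioedema and allergy (exclusions 9 and 10).

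**2. Visit items that name GBS.** Screening (Section 6): none. Day 1 (6.3.1): none; it re-asks the same criteria and so carries the same gap. Schedule of Events (15.2): none.

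**3. Reach of the time-limited criteria.**
- Exclusion 22 is the longest of the vaccine windows. Six calendar months are 181 to 184 days, depending on the date of Day 1.
- The label's interval from vaccination to GBS is up to 6 weeks: 6 × 7 = 42 days.
- Take a vaccination just outside the window with onset 42 days later. Onset then falls 181 − 42 = 139 to 184 − 42 = 142 days before Day 1, or about 4.6 to 4.7 months (139/30.4375 and 142/30.4375).
- So an episode that began roughly four and a half months or more before Day 1 can pass exclusions 20 to 22.
- It also passes exclusion 16 once any immunomodulating treatment ended more than 90 days before Day 1.
- Section 5.5 records medications from the 30 days before Screening only, so past treatment would not show up there either.

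**4. Examination.** A neurologic examination can find residual deficits. It may be normal after recovery.

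**5. What is left for an older, recovered episode.**

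| Criterion | Would it apply? |
|---|---|
| Exclusions 20 to 22 | No: vaccination too long ago |
| Exclusion 16 | No: treatment too long ago |
| Exclusions 9 and 10 | No: allergy only |
| Inclusion 2 | Only by judgement; a recovered volunteer can be in good health |
| Exclusion 26 | Only by judgement; its wording on adherence, safety assessment and consent fits loosely |

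Both remaining routes require the Investigator to know of the episode, and the protocol text contains no question that asks for it.

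**6. Use of the label in the protocol body.** The Introduction cites the insert, 1.4.3 sends it to the IRB, and 10.4.3 relies on the approved labeling for safety reports. The one numbered cross-reference to 15.3 in the body, in 3.2, supports the dose. None of these places links the label's warning to eligibility.

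**The case against.** The strongest reply is that the protocol already does what the label asks. The label does not say to exclude; it asks for a clinical decision. The protocol provides a medical history, two complete examinations that include the neurologic system, and two judgement-based criteria. The insert is an appendix, so the Investigator and the IRB had the warning in hand. Naming the label's contraindication (allergy) while leaving a warning to judgement is a coherent choice.

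Most of this stands. A reader might infer that the protocol conflicts with the label; it does not, because a warning left to judgement is consistent with a warning. A reader might also infer that no one asked about GBS. The documents do not show that: the SAP refers to an eCRF for this study, which was not supplied and may contain such a question. Nor can anything be said about what subjects were told, since the consent pages were removed and the full insert text is not readable. Finally, a reader might look for a risk figure. The documents give neither the frequency of this history nor a recurrence rate, so none is offered.

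The SAP also reports that twenty subjects were enrolled. By the date of that plan an amendment could no longer protect anyone in this trial.

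What the reply does not remove is the missing prompt. A judgement is possible only once the history is known, and the protocol text leaves that to unprompted disclosure.

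**Conclusion.** The point holds as a minor, optional safety improvement. In the protocol text, 0 of 35 criteria and no Screening or Day 1 item names GBS, while the appended label asks for a benefit-risk decision after it and Section 1.2 states no direct benefit. The named time windows could catch only a recent case. For an older, recovered episode, exclusion rests on unprompted disclosure and Investigator judgement. Followed as written, the plan could dose such a volunteer without the weighing that the label calls for ever being triggered.

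The size is small. The study plans 20 subjects, and the history is expected to be rare, though its frequency cannot be derived from the documents. Endpoints and analysis are unaffected. The conclusion assumes that the unseen eCRF adds no GBS question; if it does, most of the point falls away. Exclusion 22 is not wrong in itself. It is only the criterion nearest to the gap.

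**What to change.** Add one exclusion to the synopsis and to 4.2: 'History of Guillain-Barré syndrome within 6 weeks after any influenza vaccination'. Ask about it, with no look-back limit, in the Screening medical history (Section 6) and in the Day 1 eligibility check (6.3.1).

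The rule is deliberately stricter than the label's case-by-case decision; the stated lack of direct benefit justifies that. Because Section 6.6 allows no waiver of stated criteria except for an immediate hazard, a named exclusion also makes the decision the same for every volunteer.

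The cost is a protocol amendment with IRB submission (1.4.3), one line in two places, one question asked twice and, very rarely, one lost volunteer. Visits, samples and analysis do not change. With enrolment reported as complete, the practical use is in any later study that takes over these criteria.
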